1. PURPOSE OF STUDY

- To gain experience using Impulse Oscillometry to measure lung function in human subjects.
- To determine if airway impedance, measured by Impulse Oscillometry, is impacted by a deep inspiration maneuver in a small cohort of healthy human subjects.

2. BACKGROUND AND RATIONALE

Impulse Oscillometry (IO) is a noninvasive method of measuring respiratory mechanics and is quickly being adopted as an adjunctive test in the diagnosis and monitoring of lung disease (1). During IO, pressure oscillations are applied at the mouth during tidal breathing across a range of frequencies to measure variables of resistance and reactance (2). Unlike conventional pulmonary function testing that require modified breathing maneuvers like forced exhalation or sustained breath holding, IO is analyzed during normal tidal breathing, requires minimal cooperation by the test subject, and may be advantageous in patients who perform poorly with traditional lung function testing. IO also has the potential of detecting small changes in the periphery of the lung (3), which has generated particular interest in its clinical utility in obstructive lung disease. Resistance and reactance variables measured by IO seem to have greater sensitivity than traditional spirometry in measuring bronchodilatory response (4), which has strong implications for its use in the monitoring and treatment of airways diseases like asthma. Although IO has been investigated for decades in pulmonary physiology labs, recent improvements in technology have led to the development of handheld devices that can obtain accurate and reproducible measurements during a few minutes of tidal breathing. Consequently, there is renewed interest in incorporating IO into routine pulmonary function testing, and in fact IO is currently covered under certain CPT codes. Co-investigator [name] is the Medical Director of Pulmonary Function Labs at the URMC, and we are considering incorporating IO into our clinical testing protocols. We recently purchased a Tremoflo C-100 Oscillometer from Thorasys, Inc., and one goal of this RSRB proposal is to gain preliminary experience with this procedure and device in healthy subjects. We considered conducting pilot testing in healthy subjects as a Quality Improvement / Quality Control project, without a full proposal to the RSRB. However, we realized that we could simultaneously conduct a small scale research project, where we address an unknown question in the field: what is the effect of deep inspiration on respiratory impedance as measured by IO?

Deep inspiration (DI) has been demonstrated to have beneficial effects on the lungs of healthy subjects (5). In particular, DI performed by healthy individuals before bronchoprovocation testing results in less bronchoconstriction (6). This bronchoprotective effect of DI was not observed in patients with asthma (7), suggesting that an inability to modulate small airway smooth muscle is an important aspect of asthma pathophysiology. The bronchoprotective effect of DI has been mostly evaluated using bronchoprovocation testing with spirometry and there is limited data on the effect of deep inspiration on the oscillometry variables of resistance and reactance (8). If the bronchoprotective effect of DI

can be reliably demonstrated in healthy subjects using oscillometry, then there is potential for oscillometry to detect the absence of bronchoprotection with DI in individuals with asthma. The capability of detecting these small airway changes has strong implications in future asthma pathophysiology research. The secondary aim of this study is to evaluate whether there is a detectable difference in oscillometry variables before and after DI in healthy subjects. Thus this RSRB proposal aims to “kill two birds with one stone”, namely to: (1) gain experience with a new device to measure lung function, and (2) to determine if DI influences respiratory function as measured by IO.

4. STUDY DESIGN

- This is a single-center study that will enroll healthy subjects from a convenient study population.
- The aims of the study are to:
 - Gain experience with performing impedance oscillometry using a Tremoflo C-100 in healthy subjects.
 - Determine if there is a detectable difference in oscillometry variables before and after deep inspiration in healthy human subjects.
- Study outcomes:
 - Oscillometry measurements before and after deep inspiration to include respiratory system resistance (Rrs), respiratory system reactance (Xrs), and resonant frequency (Fres).

4.1. SUBJECT POPULATION

- Up to fifty (50) healthy subjects will be recruited from Mary Parkes Asthma and Allergy Center and the outpatient pulmonary clinics at the University of Rochester Medical Center, and from the Pulmonary and Critical Care Division at the University of Rochester.

4.2. STUDY INTERVENTIONS

- Measurement of airway impedance using the Forced Oscillation Technique
 - THORASYS® tremoflo® C-100 Airwave Oscillometry System™ (AOS)
 - This is a 510(k) FDA approved, non-significant risk device, and will be used according to FDA indication, which states: *“The tremoflo C-100 Airwave Oscillometry System is intended to measure respiratory system impedance using the Forced Oscillation Technique (FOT). tremoflo C-100 Airwave Oscillometry System is intended for use with pediatric and adult patients 4 years of age or older. The device is designed to be used by pulmonologists, general practitioners, nurses, respiratory therapists, laboratory technologists, medical researchers and similarly trained personnel in hospitals, clinics, and private physician offices”.*
 - This is a non-significant risk device because it does not require any

instrumentation or other procedures, and the subjects simply breathes normally for a few minutes into a mouthpiece while the device measures pressure at the mouth piece.

- We are not seeking approval for a new indication or new patient population for the device. Rather, in this study we are testing its effectiveness to detect differences in oscillometry before and after deep inspiration in healthy subjects.
- The device will be stored in the Department of Pulmonary and Critical Care Medicine Department Office. Only the co-investigators in this study will have access to the device. The device is portable so will be moved to the clinic locations mentioned in section 3 where testing will be performed.
- The device is handheld with a removable mouthpiece/filter attachment that is disposable. The subject places his/her mouth over the mouthpiece and breathes normally. A button is pressed on the side of the device that begins the test. Sound waves are generated at the mouth and measurements are made over several seconds. After about 20-30 seconds, the first collection of data is complete. This process is repeated at least 3 times to ensure repeatability. Once the test is complete, the removable filter is disposed.
- Data will be collected and stored using a password-protected standard laptop used only for this research project.

5. INCLUSION AND EXCLUSION CRITERIA

- Inclusion Criteria:
 - Age \geq 18
 - Vaccinated against COVID-19
 - Ability to provide informed consent
 - Willingness to perform breathing test
 - Willingness to provide basic demographic data (outlined in section 8)
 - Must be able to speak and understand English.
- Exclusion Criteria:
 - Unable to or unwilling to provide consent, perform test, or provide basic demographic data.

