6. RECRUITMENT METHODS

- Subjects will be recruited from the outpatient clinics at the University of Rochester Medical Center and the Mary Parkes Asthma Center. Recruitment flyers will be posted at multiple locations in these sites. The study will also be advertised to faculty and staff of the Pulmonary & Critical Care Medicine Division by group email and announcements at Divisional conferences. There are no plans to email individual subjects directly. Our outreach to faculty and staff of the Pulmonary & Critical Care Medicine Division is justified, because they have experience in the ordering, conduct and interpretation of pulmonary function tests, and we think many of them will be interested in participating in

the study and learning about this new way of measuring pulmonary function. We will avoid coercion by using neutral phrasing and making it clear that participation is strictly voluntary, and that there is no penalty for deciding not to participate.

- Interested participants will be asked to contact the study team members directly.
- We currently do not have the resources or infrastructure to enroll non-English speaking patients. We will re-evaluate if this changes at a future date.

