8. STUDY PROCEDURES

- Consent and testing procedure:
 - The investigator performing the test will discuss the protocol with the subject, answer all questions and obtain written consent prior to study enrollment.
 - Subjects will be instructed to refrain from taking deep breaths, sighs, or yawns, for at least 10 minutes prior to testing.
 - Data collected will include oscillometry impedance data (detailed below) and basic demographic information. Demographic information includes age, biological sex, self-reported race, and history of lung disease. All data collected will be stored on the research laptop which will be password protected. Data collected will be deidentified.

February 2022 revision:

- In addition to basic demographic information, subjects will be asked to fill out the following validated questionnaires: The Pittsburgh Vocal Cord Dysfunction Index, Asthma Control Test (ACT), the STOP-BANG Score (for obstructive sleep apnea), and the Newcastle Laryngeal Hypersensitivity Questionnaire (a measure of laryngeal symptoms).
- Mallampati score will be calculated by looking into the subject's mouth and neck circumference will be measured by using a disposable paper measuring tape.

- No data will be obtained or accessed from the medical record.
- Oscillometry will be performed as follows:
 - A new disposable mouthpiece/filter will be attached to the device.
 - A noseclip will be provided and can be self-applied by the subject.
 - The subject will then place mouth over the mouthpiece.
 - The subject will place hands over cheeks to limit upper airway artifact.
 - The subject is asked to breath normally.
 - The investigator will then press the button on the side of the device to begin data collection.
 - One run of the test is about 20-30 seconds of tidal breathing. The test will be repeated at least 3 times to ensure repeatability.
 - The subject will then be instructed to rest off of the mouthpiece and nose clips will be removed.
 - Next, the subject will be instructed to take five sequential deep breaths to maximal lung inflation (TLC) and maximal lung deflation (RV). Subjects will be encouraged to achieve maximal values (e.g. “keep going!” during inhalation, and “blow, blow blow!” during exhalation).
 - Then oscillometry will be repeated as above.
 - Once testing has concluded, the removable mouthpiece/filter will be discarded into a biohazard bin. The device and all surfaces will be wiped down with a Cavi Wipe or a Hydrogen Peroxide Wipe.

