13. SUBJECT WITHDRAWALS

- Subjects can withdraw from study participation at any time and no reason is needed.
- The investigators will otherwise include all data collected from subjects who undergo the proper consent process and who are able to perform the test.

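### The deep-inspiration question is set in healthy subjects, but no eligibility criterion requires health, so people with lung disease can enter the Pre/Post analysis and the 20-subject decision

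*Protocol*

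**What the plan says.** The target population is stated consistently. The Purpose (Section 1) refers to a small healthy cohort, and Section 4 gives the aim as "Determine if there is a detectable difference in oscillometry variables before and after deep inspiration in healthy human subjects". Section 4.1 says that up to fifty "healthy subjects will be recruited from Mary Parkes Asthma and Allergy Center and the outpatient pulmonary clinics", and from the pulmonary division. Section 4.2 says "we are testing its effectiveness to detect differences in oscillometry before and after deep inspiration in healthy subjects".

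The criteria that decide entry are in Section 5. Inclusion covers age, COVID-19 vaccination, consent, willingness to be tested and to give demographic data, and English. The whole exclusion list is "Unable to or unwilling to provide consent, perform test, or provide basic demographic data".

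Other sections bear on who enters and who is analysed:

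- Section 6, on the clinics and the asthma center: "Recruitment flyers will be posted at multiple locations in these sites". Division faculty and staff are a second source.
- Section 8: "Demographic information includes age, biological sex, self-reported race, and history of lung disease". The February 2022 revision adds the Asthma Control Test. The same section states "No data will be obtained or accessed from the medical record".
- Section 13: "The investigators will otherwise include all data collected from subjects who undergo the proper consent process and who are able to perform the test".
- The Data Analysis Plan (in Section 16) describes one Pre/Post comparison at p < 0.05 and an analysis after the first 20 subjects. Twenty more are added if p is borderline (for example between 0.05 and 0.10) or if some subjects look like responders. Nothing is restricted or split by lung disease.

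**The concern.** A vaccinated, consenting, English-speaking adult with asthma who can do the test meets every criterion in Section 5. If such people enter, the result no longer describes healthy subjects, which is the population the question names.

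The protocol's own rationale makes this matter. Section 2 reports that the bronchoprotective effect of deep inspiration was not seen in asthma, and proposes to show the effect in healthy people first so that its absence in asthma might later be detected. A mixed sample blurs that contrast and, on this reasoning, would plausibly dilute the Pre/Post difference.

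The decision after 20 subjects is exposed too. A mix of healthy and affected people could produce a group of apparent responders through composition alone, and that is one of the two triggers for enrolling 20 more.

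**Working it through.** **Text check.** The question is whether anything in the protocol turns the word healthy into a rule.

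| Place | What it does | Keeps lung disease out? |
|---|---|---|
| Sections 1, 4, 4.1, 4.2 | Name healthy subjects | States the intent; gives no definition |
| Section 5 | Lists eligibility | No |
| Section 6 | Recruits at clinics, the asthma center and among staff | No |
| Section 8 | Records lung-disease history and the Asthma Control Test; no use of the medical record | No; self-report is the only check available and it does not decide entry |
| Section 13 | Keeps data from consented subjects able to do the test | No |
| Data Analysis Plan | One comparison, one look at 20 | No |

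The protocol does not say that people with lung disease will enrol. It contains no criterion that would stop them.

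**Illustration of size.** The protocol gives no effect size, SD, power target or expected share with lung disease, so there is no stated figure to reproduce. Inputs from the protocol are n = 20 at the first look, up to 20 more, and significance at 0.05. Everything else is assumed: a two-sided paired t-test, SD of the change set to 1, a mean change of d in healthy subjects and m × d in affected subjects, and k affected among n.

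The test statistic is T = mean change / (SD of changes / √n). The average effect in the sample is d × [(n − k) + m × k] / n. For d = 0.66, n = 20, k = 5 and m = 0, this is 0.66 × 15/20 = 0.495. The value d = 0.66 was chosen because it gives about 80% power at n = 20: the noncentrality is 0.66 × √20 = 2.95. Power for mixed samples was simulated with 200,000 trials per cell.

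Power at n = 20, d = 0.66:

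| Effect in affected subjects | 0/20 affected | 2/20 | 5/20 |
|---|---|---|---|
| None (m = 0) | 80% | 70% | 52% |
| Half (m = 0.5) | 80% | 76% | 68% |
| Same (m = 1) | 80% | 80% | 80% |

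Sensitivity to d, with no effect in affected subjects:

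| d | 0/20 | 2/20 | 5/20 |
|---|---|---|---|
| 0.5 | 56% | 47% | 34% |
| 0.8 | 92% | 85% | 68% |

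**Borderline window.** With d = 0.66 and m = 0, the chance of 0.05 < p < 0.10 at the first look rises from about 8.5% with none affected to 14% with 5 of 20. With d = 0.5 it stays near 13%, so this rise depends on the assumed effect.

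**With the extension.** Take d = 0.66 and m = 0, let only the p-value window trigger 20 more, and keep the same share affected in the second 20. Overall rejection is then about 88%, 81% and 65% for 0, 2 and 5 affected per 20. The apparent-responder trigger has no numerical definition and cannot be modelled.

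**Restricting afterwards without replacement.** From the noncentral t with d = 0.66, 18 healthy subjects (20 − 2) give 75% power and 15 (20 − 5) give 66%.

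**The case against.** The best defence is that Section 4.1 is headed as the subject population and says healthy, so enrolling a known asthma patient would breach the protocol read as a whole. On that reading the fault is only that the word is not made operational. This has some force, but the word is undefined and appears in no criterion; two investigators could reasonably differ over well-controlled asthma.

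Several narrower points stand:

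- The sentence in Section 13 sits under withdrawals and may simply mean that data from subjects who do not withdraw are kept. It is supporting evidence, not proof of a deliberately broad analysis set.
- The asthma evidence in Section 2 comes from bronchoprovocation, which this study does not do. Section 2 also says that oscillometry data on deep inspiration are limited, and it does not address this effect in other lung diseases. Zero effect in affected subjects is an assumption.
- The loss from restricting the analysis is avoidable. The cap is 50, so 30 places remain beyond the first 20 and 10 beyond 40. If the restriction is set before the look, excluded subjects can be replaced.
- The study is exploratory, and Section 2 calls the deep-inspiration comparison a secondary aim. Gaining device experience is not harmed.
- An analysis plan that is not shown could split results by recorded history, and recruitment material that is not shown might mention health. Neither would change the eligibility criteria.

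**Conclusion.** The concern holds. The operative criteria do not match the population named in the aim, and following them as written can put people with lung disease into the Pre/Post test and the 20-subject decision. This rests on the text alone and needs no assumption about effect size.

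The statistical consequence is uncertain in size and direction. The power figures are illustrative and depend on an assumed effect, an assumed affected share and an assumed response in affected subjects; across the cases shown, the loss runs from nothing to about 28 percentage points at n = 20 (80% to 52%). Each subject is their own control, so the problem is who the result applies to and possible dilution, not confounding between groups. It should be fixed, but it does not by itself invalidate the study.

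**What to change.** Choose one of two routes.

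1. Add an exclusion to Section 5 for self-reported history of asthma, COPD or other chronic lung disease, and apply it at screening.
2. If such volunteers are wanted for device experience, state in Section 13 and the Data Analysis Plan that the deep-inspiration Pre/Post analysis, the count of 20 and any further 20 use only subjects without that history, with the others summarised separately. Set this before the first look so that the count of 20 is filled with eligible subjects under the cap of 50.

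The cost is a short protocol amendment. The history is already collected by self-report. Recruitment from the clinics may be slightly slower, but division faculty and staff remain available.

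A separate, minor matter can go into the same amendment: Section 9.2 relies on screening for transmissible respiratory infection, while Sections 5 and 8 contain no matching criterion or step. These sections should be reconciled. This does not bear on the Pre/Post analysis.

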6. RECRUITMENT METHODS

- Subjects will be recruited from the outpatient clinics at the University of Rochester Medical Center and the Mary Parkes Asthma Center. Recruitment flyers will be posted at multiple locations in these sites. The study will also be advertised to faculty and staff of the Pulmonary & Critical Care Medicine Division by group email and announcements at Divisional conferences. There are no plans to email individual subjects directly. Our outreach to faculty and staff of the Pulmonary & Critical Care Medicine Division is justified, because they have experience in the ordering, conduct and interpretation of pulmonary function tests, and we think many of them will be interested in participating in

the study and learning about this new way of measuring pulmonary function. We will avoid coercion by using neutral phrasing and making it clear that participation is strictly voluntary, and that there is no penalty for deciding not to participate.

- Interested participants will be asked to contact the study team members directly.
- We currently do not have the resources or infrastructure to enroll non-English speaking patients. We will re-evaluate if this changes at a future date.

7. CONSENT PROCESS

- The investigator will review the details of the study with the subject in person or by phone call.
- The subject will have the opportunity to read the consent form fully and ask questions. The subject may wish to consider the study further and can be given a copy of the informed consent to take home for review.
- The investigator will review with the patient that participation in the study is entirely voluntary. The subject will be informed that the decision to not participate in the study will not affect the subject's personal or professional relationship with the investigator.
- The consent process is as follows: the consent will be distributed only as a paper copy for simplicity. The subject will be presented a paper copy of the consent at the time of testing. The consent will be reviewed in its entirety with the subject. If the subject agrees to proceed, he or she may sign two copies. One copy will be sent home with the subject and the other copy will be locked in the Pulmonary & Critical Care Fellow's Office.

8. STUDY PROCEDURES

- Consent and testing procedure:
 - The investigator performing the test will discuss the protocol with the subject, answer all questions and obtain written consent prior to study enrollment.
 - Subjects will be instructed to refrain from taking deep breaths, sighs, or yawns, for at least 10 minutes prior to testing.
 - Data collected will include oscillometry impedance data (detailed below) and basic demographic information. Demographic information includes age, biological sex, self-reported race, and history of lung disease. All data collected will be stored on the research laptop which will be password protected. Data collected will be deidentified.

February 2022 revision:

- In addition to basic demographic information, subjects will be asked to fill out the following validated questionnaires: The Pittsburgh Vocal Cord Dysfunction Index, Asthma Control Test (ACT), the STOP-BANG Score (for obstructive sleep apnea), and the Newcastle Laryngeal Hypersensitivity Questionnaire (a measure of laryngeal symptoms).
- Mallampati score will be calculated by looking into the subject's mouth and neck circumference will be measured by using a disposable paper measuring tape.

- No data will be obtained or accessed from the medical record.
- Oscillometry will be performed as follows:
 - A new disposable mouthpiece/filter will be attached to the device.
 - A noseclip will be provided and can be self-applied by the subject.
 - The subject will then place mouth over the mouthpiece.
 - The subject will place hands over cheeks to limit upper airway artifact.
 - The subject is asked to breath normally.
 - The investigator will then press the button on the side of the device to begin data collection.
 - One run of the test is about 20-30 seconds of tidal breathing. The test will be repeated at least 3 times to ensure repeatability.
 - The subject will then be instructed to rest off of the mouthpiece and nose clips will be removed.
 - Next, the subject will be instructed to take five sequential deep breaths to maximal lung inflation (TLC) and maximal lung deflation (RV). Subjects will be encouraged to achieve maximal values (e.g. “keep going!” during inhalation, and “blow, blow blow!” during exhalation).
 - Then oscillometry will be repeated as above.
 - Once testing has concluded, the removable mouthpiece/filter will be discarded into a biohazard bin. The device and all surfaces will be wiped down with a Cavi Wipe or a Hydrogen Peroxide Wipe.
 - Only individuals vaccinated against the COVID-19 virus will be included in this study. This study will follow all University of Rochester Medical Center guidelines in regards to Universal Precautions for individuals vaccinated against the COVID-19 virus.
 - Note that the IO procedure is not considered aerosol-generating, and no special procedures are needed to perform the maneuver in COVID vaccinated subjects (personal communication from [name], UR Infection Prevention, 6/24/21).
- **Data storage:** All oscillometry data will be deidentified and downloaded to the research laptop. All demographic data will be deidentified and entered into the research laptop. At the conclusion of the data collection phase of the study, the deidentified data will be analyzed on the laptop using Microsoft Excel.
- **Medical Record:** Since this study is exploratory in nature, we do not plan to record subject’s participation in this study, or any IO results, in the subject’s electronic health record.

